Clinical Study Protocol		
Investigational Product	ZYN®	
Study Code	SM 17-03	
Protocol Version and Date	Final 1.0, 05Oct2017	

STUDY TITLE

Nicotine pharmacokinetics and subjective effects of a single dose of a non-tobacco-based nicotine pouch (ZYN®) compared with conventional, tobacco-based Swedish snus among current, daily snus users.

Design	Open, randomized, five-way cross-over, single dose administration. The study will include 18 subjects.
Test products and dosage	 1= ZYN Smooth containing 3 mg nicotine per portion 2= ZYN Smooth containing 6 mg nicotine per portion 3= ZYN Smooth containing 3 mg nicotine per portion (alternative manufacturing process)
	4= ZYN Smooth containing 6 mg nicotine per portion (alternative manufacturing process)
Comparator product and dosage	5= Swedish portion snus PSWL 1.0 g (8 mg nicotine/g)
Sponsor signatory	Swedish Match [name] [name]

Principal Investigator

[name], PhD CTC Clinical Trial Consultants AB

Clinical study conduct and management

CTC Clinical Trial Consultants AB [name]

Amendment No.	Date of Amendment	Revised protocol version (if applicable)

The following amendments have been made to the Final Clinical Study Protocol version 1.0:

2 STUDY SYNOPSIS

Study Title

Nicotine pharmacokinetics and subjective effects of a single dose of a non-tobacco-based

nicotine pouch (ZYN®) compared with conventional, tobacco-based Swedish snus among current, daily snus users.

Study code

SM 17-03

Study period

Estimated date of first subject enrolled:

Q4 2017

Estimated date of last subject completed:

Q1 2018

Principal Investigator

[name], PhD CTC Clinical Trial Consultants AB

Study design

Open, randomized, five-way cross-over, single dose administration.

Objectives

Primary objective(s)

To compare each subject's AUC_{inf} based on plasma concentrations of nicotine after administration of one single dose of a novel, non-tobacco-based nicotine pouch containing 3 and 6 mg of nicotine, to that of one single dose from a 1 g Swedish snus pouch containing 8 mg of nicotine.

Secondary objectives

- 1. To compare AUC_{60min} , C_{max} , T_{max} , AUCo-t and terminal half-life of a novel, non-tobacco-based nicotine pouch to that of a Swedish snus pouch.
- 2. To compare the estimated *in-vivo* extracted amount of nicotine from a novel, non-tobacco-based nicotine pouch containing 3 and 6 mg of nicotine, respectively, with that from a 1 g Swedish snus pouch containing 8 mg of nicotine.
- 3. To compare heart rate and subjective effects ("head buzz") after study product administration (as proxy for *in vivo* nicotine uptake).
- 4. Collection of adverse events

Number of subjects planned

The study will include 18 subjects.

Diagnosis and main eligibility criteria

Healthy subjects aged ≥ 19 years who use tobacco-based snus since ≥ 1 year with a weekly consumption of three or more snus cans (brands with nicotine content $\leq 1\%$) or two or more cans (brands with nicotine content $\geq 1\%$). Subjects who are pregnant or who have a history of hypertension or any cardiovascular disease are excluded. Subjects shall be abstinent from snus and all other nicotine containing products from 8.00 p.m. the night before each trial day.

Methodology

Before entry to the study subjects undergo screening evaluations including medical history and pulse rate measurements before/after application of their usual brand of Swedish snus.

Subjects report to the clinic on separate days for the 5 experimental sessions. The subjects are instructed to abstain from snus or other nicotine delivery products as from the evening before and smoking 24 hours prior to all visits to the clinic. All sessions are performed during the morning hours to facilitate abstinence. The subjects should certify abstinence before each treatment is started.

The treatments are administered as single doses in a pre-determined randomized order. The subject keeps the pouch still between the upper lip and the gum for 60 minutes and are instructed not to manipulate the pouch with the tongue or lips. The subjects are instructed not to eat or drink from 30 minutes before and during application of investigational products and 30 minutes after the investigational product have been taken out. [5].

Each used pouch is collected and frozen $(-20^{\circ}C)$ pending analyses of nicotine. Unused pouches are collected and frozen $(-20^{\circ}C)$ pending analysis and serve as references in the calculations of extracted doses.

Investigational Products, dosage and mode of administration

Test articles:

1= ZYN Smooth containing 3 mg nicotine per portion

2= ZYN Smooth containing 6 mg nicotine per portion

3= ZYN Smooth containing 3 mg nicotine per portion (alternative manufacturing process)

4= ZYN Smooth containing 6 mg nicotine per portion (alternative manufacturing process)

Reference articles:

5= Swedish portion snus PSWL 1.0 g (8 mg nicotine/g)

Duration of treatment

The treatments are administered as single doses in a pre-determined randomized order. The subject keeps the pouch still between the upper lip and the gum for 60 minutes. Plasma concentrations of nicotine are followed over 6 hours.

Duration of subject's involvement in the study

Each Subject will participate in the study approximately 20-84 days.

Efficacy assessments

Pharmacokinetics assessments - WinNonlin computer program (Certara Corp., USA) will be used for pharmacokinetic calculations. Nicotine plasma concentrations are determined at preset time points, before *(0), 5, 10, 15, 30 and 60* minutes, 1.5, 2, 4 and 6 hours after administration.

Pulse rate – Pulse rate will be measured at the following time points: before (0), 5, 10, 15, 30 and 60 minutes after each product is administered.

Subjective effects – Each subject's rating of product "strength" using a Visual Analogue Scale (VAS): (head "buzz", "head rush", "hit", feeling alert, overall "product strength"), anchored with "not at all" to "extremely". VAS scores will be obtained at the following time points before (0), 5, 10, 15, 30 and 60 minutes after each product is administered.

Safety assessments

Adverse Events will be collected starting with administration of the Investigational Product until the last follow-up from the first dose.

Statistical methods

The study will include 18 subjects. A previous study (Lunell E & Curvall M 2011) has made the calculation of sample size possible. Nicotine extraction from 1 g Swedish portion snus containing 8 mg nicotine/pouch was estimated at 2.18 ± 0.92 mg per 1 g portion. Under the assumption of a complete dissolution and extraction of the 3 and 6 mg ZYN® products, respectively, versus the 2.18 ± 0.92 mg nicotine, and a standard deviation of 5.0 the estimated sample size is 16 with a power of 80% and alpha=0.05.

3 TA	BLE OF CONTENTS	
2 STU	UDY SYNOPSIS	4
3 TA	BLE OF CONTENTS	7
4 LIS	T OF ABBREVIATIONS AND DEFINITIONS OF TERMS	11
5 IMI	PORTANT MEDICAL PROCEDURES TO BE FOLLOWED BY THE	
	INVESTIGATOR	
5.1	Medical emergencies contacts	13
	Overdose	
6 INV	/ESTIGATOR(S) AND STUDY ADMINISTRATIVE STRUCTURE	
6.1	.1 Investigational Product manufacturing and packaging	15
6.1		
7 INT	RODUCTION	16
7.1	Project background	16
7.2	Investigational products	17
7.2	2.1 Product characteristics	17
7.3	Risk/benefit assessment	17
7.3	S.1 Summary of risk management	17
8 STU	UDY OBJECTIVES AND ENDPOINTS	18
8.1	Primary objective(s)	18
8.1	.1 Primary endpoint (s)	18
8.2	Secondary objectives	18
8.2	2.1 Secondary endpoints	18
9 INV	/ESTIGATIONAL PLAN	19
9.1	Overall study design and schedule of events	19
9.2	Rationale for study design and dose groups	21
10 ST	CUDY POPULATION	21
10.1	Recruitment	21
10.2	Screening and enrolment log	21
10.3	Number of subjects	21
10.4	Inclusion criteria	21
10.5	Exclusion criteria	22
10.6	Restrictions during the study	22
10.7	Criteria for subject withdrawal	23
10.	7.1 General withdrawal criteria	23
10.	7.2 Procedures for discontinuation of a subject from the study	23
CONFI	DENTIAL 7 (45)	

10.7	.7.1 Subject replacement	23
10.8	Randomization	24
10.9	Blinding	24
11 TR	REATMENTS	24
11.1	Identity of investigational products	24
11.2	Packaging and labelling	24
11.3	Conditions for storage	24
11.4	Dispensing and accountability	24

4 LIST OF ABBREVIATIONS AND DEFINITIONS OF TERMS

Abbreviation or term	Explanation
AE	Adverse event
ATC	Anatomical therapeutic chemical
BP	Blood pressure
CRF	Case report form
CSP	Clinical study protocol
CSR	Clinical study report
CTC	Clinical Trial Consultants AB
CTCAE	Common terminology criteria for adverse events
CV	Coefficient of variation
DMP	Data management plan
DVP	Data validation plan
EEA	European Economic Area
GCP	Good clinical practice
h	hour
ICF	Informed consent form
ICH	International conference on harmonization
IEC	Independent ethics committee
IP	Investigational product
MedDRA	Medical dictionary for regulatory activities
min	minute
Ν	number
NRT	Nicotine replacement therapy
NSAID	Non-steroid anti-inflammatory drug
SAR	Serious adverse reaction
PPAS	Per protocol analysis set
PSWL	Pouched Snus White portion Large
PT	Preferred term
SADR	Serious adverse drug reaction
SAE	Serious adverse event
SAP	Statistical analysis plan
SD	Standard deviation
CONFIDENTIAL	11 (45)

SDV	Source data verification
sec	Second
SOC	System organ class
SOP	Standard operating procedures
SUSAR	Suspected unexpected serious adverse reaction
TEAE	Treatment emergent adverse event
VAS	Visual Analogue Scale
WHO	World Health Organization

5 IMPORTANT MEDICAL PROCEDURES TO BE FOLLOWED BY THE INVESTIGATOR

5.1 Medical emergencies contacts

The Principal Investigator is responsible for ensuring that procedures and expertise are available to handle medical emergencies during the study. A medical emergency usually constitutes a serious adverse event (SAE) and is to be reported as such. Detailed SAE reporting procedures are included in Section 12.6.5.

In the case of a medical emergency the Investigator may contact the Medical Responsible Person at Swedish Match.

5.2 Overdose

An overdose is a dose in excess of the dose specified for each cohort in this clinical study protocol (CSP).

Over-dosing is not likely to occur in this study since all investigational products will be administered by site personnel under medical surveillance. In cases of accidental overdose, standard supportive measures should be adopted as required (see Section 7.3.1).

Overdose should be recorded as follows:

- An overdose with associated adverse event (AE) is recorded as the AE diagnosis/symptoms on the relevant AE modules in the case report form (CRF).
- An overdose without associated symptoms is only reported in the subject's medical records.

6.1.1 Investigational Product manufacturing and packaging

The investigational and reference products will be manufactured and packaged compliant with Swedish law on food production. The investigational and reference products will be transferred from the original container, weighed and individually packaged in identical sealed food approved test containers at Swedish Match analytical lab.

6.1.2 Identity of investigational products

Each dose of the investigational and reference products will be delivered in separate identical food approved glass containers labeled with unique identification numbers.

Signatures required are provided in Appendix 18.1.

7 INTRODUCTION

7.1 Project background

Sweden displays the lowest prevalence of smoking in Europe, particularly among males. Population surveys have indicated that snus is the most frequently used smoking cessation aid. Snus is sometimes used as a last resort for people who have failed stopping smoking with the available, pharmaceutical smoking cessation aids. Smokeless tobacco is capable of rapidly delivering nicotine to the bloodstream (Fant et al 1999), and therefore may be more satisfactory among smokers than currently available pharmaceutical nicotine products. Traditionally there has been no non-tobacco-based nicotine product on the Swedish market intended for recreational use similar to Swedish snus. Despite the vast risk differential between snus and cigarettes in terms of adverse long-term health effects including cancer, cardiovascular disease and chronic lung disease, snus remains a controversial product as it contains tobacco and is intended for recreational use. The tobacco component of snus explains why it contains measurable amounts of hazardous constituents such as potentially carcinogenic nitrosamines, albeit at very low concentrations.

Recently, a novel, non-tobacco-based nicotine product (ZYN®) has been developed. It has some features that are similar to snus: it comes in pouches with a nicotine content of 3 or 6 mg; it is used the same way as snus, that is, it is placed under the upper lip. In contrast to snus the product contains no nitrosamines or polycyclic hydrocarbons (PAHs), which are the two main classes of unwanted substances in snus that are classified as potentially carcinogenic. Other unwanted substances in ZYN® are present in comparable or lower concentrations than in snus. The toxicological safety profile of ZYN® thus represents a significant improvement over snus with the exception of the nicotine content which is only marginally lower than in snus (3 or 6 mg in ZYN® versus e g 8-12 mg in a conventional 1.0 g snus pouch).

Commercially available snus products have a nicotine content ranging between 1-2%. Previous studies (Lunell E and Curvall M 2011), have indicated that on average about 15-20% of the total nicotine content is extracted and absorbed, with large inter-individual variation. Extraction is generally not linear with pouch size: surface area, saliva penetration and diffusion factors may be important determinants of nicotine uptake.

The nicotine delivery profile of a tobacco-free product like ZYN® is probably a main determinant of its efficacy to function as an alternative to cigarettes and snus. In view of these circumstances, it is highly justified to study the nicotine delivery profile of ZYN® in comparison with commercially available snus products (which have a documented ability to replace cigarettes as a source of recreational nicotine among current tobacco consumers). The Sponsor has previously conducted studies of nicotine chewing gum with different nicotine content versus snus products. We now intend to extend those observations by comparing the ZYN® product with Swedish snus.

The main aim of the present study is to document the *in-vivo* extraction of nicotine from ZYN® pouches and the resulting uptake to the systemic blood circulation, measured as AUC_{inf}, based on plasma concentrations of nicotine, versus a conventional snus pouch. The extraction and plasma data will be supplemented with assessments of subjective effects of "product strength" and pulse rate measurements, both of which constitute proxies for systemic nicotine uptake.

7.2 Investigational products

7.2.1 Product characteristics

Test and reference products will be delivered in identical containers labeled with unique identification numbers.

The test product of non-tobacco-based nicotine contains 3 and 6 mg of nicotine, respectively, in a pouch.

The reference product of 1 g Swedish snus pouch contains 8 mg of nicotine. Administration of the pouch will be between the upper lip and the gum.

7.3 Risk/benefit assessment

It may be considered problematic to expose research subjects to a novel nicotine delivery product the properties of which are not yet fully known. However, all research subjects are required to be daily snus users since at least one year (with an average or above snus consumption) so the participants are well acquainted with and used to the effects of nicotine. Preliminary data from the manufacturer ([name], personal communication) indicate that the amount of nicotine extracted from the test articles is comparable to that from tobaccobased snus, despite the fact that the overall nicotine content and content of free nicotine in the ZYN® pouches, 3 and 6 mg, is lower than in conventional tobaccobased snus (8 mg). This suggests that adverse effects from the nicotine exposure from the test and reference articles are unlikely to occur among the research subjects.

Aside from the nicotine, all ingredients used in the test products are food-approved (similar to ingredients in conventional snus). The nicotine in ZYN® is of pharmaceutical grade, i.e. the same as the nicotine in nicotine replacement products (gum, lozenges, mouth spray etc.). ZYN® is currently commercially available on the U.S. and Swedish markets.

The study does not involve invasive procedures, beside the collection of venous blood samples. So far, no adverse effects have been reported associated with the use of ZYN® apart from effects likely to be related to the nicotine exposure (such as salivation, nausea, and dyspepsia).

Pregnant women or individuals with a history of hypertension or any cardiovascular disease, who may be particularly vulnerable to nicotine exposure, are excluded from participation.

The potential adverse effects of the study procedures, which are likely to be minor and/or clinically insignificant, are from a research ethics perspective counterbalanced by the potential positive effects of the novel nicotine pouch as a reduced toxicity alternative to conventional snus. As the nicotine delivery profile of a product is likely to be central to its acceptability among current tobacco users, it is reasonable to conduct formal clinical studies to assess this feature in more detail.

7.3.1 Summary of risk management

Subjects will remain in the research clinic for 6 hour after the administration of the Investigational Product and will be closely monitored by medical staff.

8 STUDY OBJECTIVES AND ENDPOINTS

8.1 Primary objective(s)

To compare each subject's AUC_{inf} based on plasma concentrations of nicotine after administration of one single dose of a novel, non-tobacco-based nicotine pouch containing 3 and 6 mg of nicotine, to that of one single dose from a 1 g Swedish snus pouch containing 8 mg of nicotine.

8.1.1 Primary endpoint (s)

 AUC_{inf} based on plasma concentrations of nicotine after administration of one single dose of a novel, non-tobacco-based nicotine pouch containing 3 and 6 mg of nicotine, to that of one single dose from a 1 g Swedish snus pouch containing 8 mg of nicotine.

8.2 Secondary objectives

- 1. To compare AUC_{60min} , C_{max} , T_{max} , AUCo-t and terminal half-life of a novel, non-tobacco-based nicotine pouch to that of a Swedish snus pouch.
- 2. To compare the estimated *in-vivo* extracted amount of nicotine from a novel, non-tobacco-based nicotine pouch containing 3 and 6 mg of nicotine, respectively, with that from a 1 g Swedish snus pouch containing 8 mg of nicotine.
- **3.** Comparison of pulse rate and subjective effects ("head buzz") after study product administration (proxy for *in vivo* nicotine uptake).
- 4. Adverse events
- 8.2.1 Secondary endpoints
 - 1. AUC_{60min}, C_{max}, T_{max}, AUCo-t and terminal half-life of a novel, non-tobacco-based nicotine pouch to that of a Swedish snus pouch.
 - 2. In-vivo extracted amount of nicotine
 - 3. To assess the correlation between the estimates of AUC(inf) and the total amount of nicotine extracted from the ZYN® pouches.
 - 4. Pulse rate and VAS for measure "head buzz" (head rush, "hit", feeling alert, overall "product strength"), using a 100-mm visual analogue scale (VAS) anchored with "not at all" to "extremely" at preset time points up to 60 minutes (predose, + 5min, +10 min, +15 min, +30 min, +60 min after each dose), respectively, after study product administration (proxy for systemic uptake).
 - 5. Collection of adverse events

9 INVESTIGATIONAL PLAN

9.1 Overall study design and schedule of events

The study will be conducted as an open, randomized, five-way cross-over, single dose administration. The study will include 18 subjects.

The subjects included will be healthy males and females aged ≥ 19 years who use tobaccobased snus, since ≥ 1 year with a weekly consumption of three or more snus cans (brands with nicotine content $\leq 1\%$) or two or more cans (brands with nicotine content $\geq 1\%$). Subjects who are pregnant or who have a history of hypertension or any cardiovascular disease are excluded. Subjects shall be abstinent from snus and all other nicotine containing products from 8.00 p.m. the night before each trial day.

Before entry to the study subjects undergo screening evaluations including smoking and snus use, medical history and pulse rate measurements before/after application of their usual brand of snus. The puls rate assessment will be made in abstinent condition from 8 p.m. the night before.

A pulse rate increase of ≥ 10 beats/min in the morning before use of any nicotine containing product will classify the subject as eligible for participation the study.

Subjects report to the clinic on separate days for the 5 experimental sessions. The subjects are instructed to abstain from snus, cigarettes or other nicotine delivery products as from 8 pm the evening before. All sessions are performed during the morning hours to facilitate abstinence. The subjects should certify abstinence before each treatment is started.

The treatments are administered as single doses in a pre-determined randomized order. The subject keeps the pouch still between the upper lip and the gum for 60 minutes and are instructed not to manipulate the pouch with the tongue or lips. The subjects are instructed not to eat, drink, chew chewing gum or brush teeth from 30 minutes before application of treatment, during application of investigational products and 30 minutes after the investigational product have been taken out. [5].

Each used pouch is collected and frozen (-20°C) pending analyses of nicotine.

Assessment	Screening	Cross-over phase	Follow-up Phone contact
	Visit 1 ¹	Visit 2-6 ²	Visit 7
	Day -14 to -1	Day 1 followed by 1-14 day(s) of wash-out. Repeated for each dose time point	7 Days after last dose – 3/+7 days
Informed consent	Х		
Eligibility	Х	X ⁸	
Demographics	Х		
Prior and Concomitant medication	Х	X	X
Medical history	Х		
Urine pregnancy test ³	Х		
HIV, Hepatitis B and C test	Х		
Drug screen	X ⁴	X ⁴	
CO measurement	Х	X	
Pulse rate	X ⁵	X ⁶	
Visual Analogue Scale		X ⁶	
Investigational Product administration		X	
Collection of pouches		X	
PK blood sampling		X ⁷	
Baseline Symptoms	Х	X ⁸	
Adverse Events		X	X

Table 1 Overall Schedule of Events

¹ Visit 1 could be performed during 2 days

² Refer to Schedule of Events per visit for details.

³ Female subjects only

⁴ Drug tests during the treatment period may be performed randomly.

⁵ Before and 15 min after application of the subject's usual brand and amount of Swedish snus

⁶ Before and 5, 10, 15, 30 and 60 min after application of the investigational products

⁷ Before and 5, 10, 15, 30, 60, 90, 120, 240 and 360 min after application of the investigational products

⁸ Only prior to dose administration on visit 2.

9.2 Rationale for study design and dose groups

Pouched Swedish snus has recently been studied in a report by Lunell and Curvall (2011). The snus investigated in that report, Swedish portion snus PSWL 1.0 g (8 mg nicotine/g), released an average 2.18 mg nicotine following use over 30 minutes. Non-tobacco-based products with similar nicotine content are investigated in the present study. The rationale for the choice of the 3 mg and 6 mg dose of the non-tobacco-based nicotine pouch is that 6 mg proved safe in a previous study (Molander L and Lunell E 2001). In view of these circumstances, it is highly justified to study the nicotine delivery profile of the non-tobacco-based nicotine pouch (ZYN®) in comparison with commercially available snus products. We thus intend to extend those observations by comparing a nicotine non-tobacco-based nicotine pouch (ZYN®) with Swedish snus, PSWL 1.0 g (8 mg nicotine/g).

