12.5.3 Collection of pouches and analysis

Pouches for the determination of nicotine after administration of the Investigational Product will be collected after 60 minutes (see Overall study design and schedule of events in Section 9.1). The following time window will apply for the pouch sampling:

 $- \pm 1$ min.

- The date and time of collection of each pouch will be recorded in the CRF.

All the collected pouches will be collected and frozen immediately at -20°C.

Pouches for extraction of nicotine will be analyzed by Swedish Match. Pouches from all evaluable subjects excluding withdrawn or dropout subjects will be analyzed.

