17.2 Determination of sample size

The primary endpoint is nicotine extraction. The study will include 18 subjects. A previous study [Lunell E & Curvall M 2011] has made the calculation of sample size possible. Nicotine extraction from a 1 g Swedish portion snus (PSWL) containing 8mg nicotine/pouch was estimated at 2.18 ± 0.92 mg per portion. Under the assumption of a complete dissolution and *in-vivo* extraction of the 3 and 6 mg ZYN® products, respectively, versus the 2.18 ± 0.92 mg nicotine, and a standard deviation of 5.0 the estimated sample size is 16 with a power of 80% and alpha=0.05. The randomization will be performed using Latin Squares approach.

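### The stated sample size rests on a 30-minute snus extraction value, while every pouch in this trial is used for 60 minutes, so the claimed 80% power is unsupported

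*Protocol*

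**What the plan says.** **Source of the snus value.** Section 9.2 reports that the reference snus, in the earlier study, "released an average 2.18 mg nicotine following use over 30 minutes". Section 17.2 then states: "Nicotine extraction from a 1 g Swedish portion snus (PSWL) containing 8mg nicotine/pouch was estimated at 2.18 ± 0.92 mg per portion". The synopsis uses the same figure. Neither 17.2 nor the synopsis mentions how long the pouch was used.

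**Use time in this trial.** Section 9.1: "The subject keeps the pouch still between the upper lip and the gum for 60 minutes". Section 12.5.3 says that pouches for the nicotine determination "will be collected after 60 minutes", with a window of ±1 minute. Both apply to all five products.

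**Expected extraction from ZYN.** The calculation in 17.2 begins "Under the assumption of a complete dissolution and" extraction of the 3 and 6 mg pouches. It uses an SD of 5.0 and arrives at 16 subjects for 80% power at alpha 0.05; 18 are to be included. Section 7.3 cites preliminary manufacturer data which "indicate that the amount of nicotine extracted from the test articles is comparable to that from tobaccobased snus", and section 14.2 repeats this. Neither section gives a figure.

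**The concern.** The sample-size calculation compares what is expected to leave a ZYN pouch with what is expected to leave a snus pouch. The snus side is a 30-minute value, but the trial will measure 60-minute extraction. At 30 minutes, 2.18 of 8 mg (27%) has been released and 73% is still in the pouch, so further release is plausible. Carrying 2.18 mg over unchanged assumes that there is none, and the protocol neither states nor supports this. Any further release narrows the 6 mg difference and lowers the power claimed.

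On the other side of the comparison, complete extraction of the 6 mg pouch means 2.75 times the snus value used. The risk and ethics sections describe extraction as comparable to snus and argue from this that adverse effects are unlikely. For the 6 mg pouch, the sample-size section and the risk section therefore appear to expect different exposures from the same product.

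**Working it through.** **Inputs.** From 17.2: snus 2.18 mg (SD 0.92), ZYN 3 and 6 mg fully extracted, SD 5.0, 80% power, alpha 0.05, stated n = 16. From 17.1: two-sided tests. From 10.3: 18 subjects. From 9.2, 9.1 and 12.5.3: 30 minutes behind the 2.18 mg, 60 minutes here. The protocol gives neither a 60-minute snus value nor a ZYN extraction fraction from data, so the 60-minute values below are assumptions.

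**Method.** Paired t-test on within-subject differences. Power comes from the noncentral t distribution with n − 1 degrees of freedom and noncentrality (difference / SD) × √n.

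**Step 1: reproduce the plan's figure.**
- 6 mg contrast: 6 − 2.18 = 3.82 mg, SD 5.0. Required n = 16, with power 81.5% at 16 and 86% at 18. The stated figure reproduces.
- 3 mg contrast: 3 − 2.18 = 0.82 mg, SD 5.0. Required n = 294, with power 10% at 18. The stated figure does not reproduce.

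So 16 comes from the 6 mg contrast alone, and the snus value enters it directly.

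**Step 2: assumed range for snus at 60 minutes.**
- No further release: 2.18 mg.
- First-order release: fraction at 30 minutes 2.18/8 = 0.2725; at 60 minutes 1 − (1 − 0.2725)² = 0.471; 8 × 0.471 = 3.77 mg.
- Linear release: 2 × 2.18 = 4.36 mg.

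**Step 3: 6 mg contrast at the protocol's SD of 5.0.**

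| Snus at 60 min (mg) | Difference (mg) | Power, n = 16 | Power, n = 18 | n for 80% |
|---|---|---|---|---|
| 2.18 | 3.82 | 81% | 86% | 16 |
| 2.50 | 3.50 | 75% | 80% | 19 |
| 3.00 | 3.00 | 61% | 67% | 24 |
| 3.77 | 2.23 | 39% | 43% | 42 |
| 4.36 | 1.64 | 23% | 26% | 75 |

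The second row is just under 80% at 18 (79.9%). Eighteen subjects give 80% power only for a difference of about 3.5 mg or more, that is, a 60-minute snus value of no more than about 2.5 mg if the 6 mg pouch is fully extracted.

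**Step 4: how far this depends on the SD.** The SD of 5.0 has no stated source and is 5.0/0.92 = 5.4 times the only SD quoted. As an illustration, assume equal SDs of 0.92 for both products and no correlation; the SD of the difference is then 0.92 × √2 = 1.3 mg. For the 6 mg contrast at 18 subjects, power exceeds 99% at both 2.23 and 1.64 mg. At an intermediate assumed SD of 2.0, it is 99% and 91%.

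For the 3 mg contrast, an SD of 1.3 gives 71% power at 18 for 0.82 mg. Its expected direction also depends on the snus value: 3 − 3.77 = −0.77 mg and 3 − 4.36 = −1.36 mg, against +0.82 mg as planned.

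**Step 5: complete against comparable extraction.** On the 2.18 mg value, complete extraction gives 6/2.18 = 2.75 times snus for the 6 mg pouch and 3/2.18 = 1.38 times for the 3 mg pouch. On the assumed 60-minute values, the 6 mg ratio falls to 6/3.77 = 1.59 or 6/4.36 = 1.38, and the 3 mg ratio to 0.80 or 0.69.

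**The case against.** The strongest reply is that nothing has been miscalculated: 16 follows from the inputs given. That is right. The fault lies in the planning inputs, not in the arithmetic.

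A second reply is that the power losses in Step 3 are produced by an SD that is itself doubtful. This also stands. A reader might infer from the 43% and 26% that the trial is underpowered on extraction. The protocol does not support that, because with a within-subject SD nearer to the one it quotes, the 6 mg contrast would be well powered across the whole assumed range.

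A third reply concerns complete and comparable extraction. A reader might infer that the two statements cannot both be true. That goes too far. Complete extraction is labelled an assumption, and the word comparable rests on preliminary data with no figure. For the 3 mg pouch the gap of 0.82 mg is smaller than the quoted snus SD of 0.92. For the 6 mg pouch, a higher 60-minute snus value would shrink the ratio from 2.75 to about 1.4 to 1.6, so correcting the first problem eases the second. What remains is unreconciled wording for the 6 mg pouch. It would likewise be too strong to read comparable as exactly equal and conclude that power is about 5%, because the protocol claims no equality.

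Finally, 17.2 concerns extraction, which it calls the primary endpoint, while 8.1.1 and 17.5 name AUCinf. Better extraction inputs would still say nothing about power for AUCinf. That limits the consequence, but it does not make the mismatched input right.

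**Conclusion.** The point holds as one about planning inputs. The protocol's own text shows that the snus mean behind the sample size is a 30-minute value used without qualification for a 60-minute trial, and that the stated 16 depends on it through the 6 mg contrast only. At SD 5.0 and 18 subjects, power for that contrast is 86% if release stops at 30 minutes, 43% under first-order release and 26% under linear release. The release patterns are assumptions and the SD is unexplained, so these figures show how fragile the stated 80% is. They do not estimate the trial's actual power.

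The difference in wording on ZYN extraction is a secondary matter: clear enough to need reconciling for 6 mg, weak for 3 mg. Correction is advisable, but no conclusion about the design follows from it alone.

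**What to change.** - In 17.2 and the synopsis, label 2.18 mg as a 30-minute value.
- Redo the calculation with a 60-minute snus value or, if none exists, a stated range, and with a within-subject SD whose source is given.
- Report power as a range for each contrast at 18 subjects, and say that 16 comes from the 6 mg contrast only.
- Reconcile the extraction expected from the 6 mg pouch in 17.2 with the wording in 7.3 and 14.2, so that all three sections use one expectation.

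The cost is a short protocol amendment and a rerun of a simple calculation. The number of subjects and the trial procedures need not change. At SD 5.0 the restated power would be less favourable; with a smaller, justified SD it may not be.
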